### **11.3. Randomization Methods**

Not applicable as being a non-randomized study.

### **11.4. Interim Analysis**

No interim analysis is planned; however, the Period 1 analyses (both primary and secondary) will be analyzed once the last patient has completed the 4-week treatment period.

### **11.5. Handling of dropouts or missing data**

As a general approach, no missing data imputation is planned for the study; however, it will be further concreted in the Statistical Analysis Plan (SAP).

### **11.6. Multiple Comparisons/ Multiplicity**

No adjustments for multiplicity of assessments will be considered.

### **11.7. Examination of subgroups**

No specific subgroup of patients analysis is planned; however, it will be further concreted in the Statistical Analysis Plan (SAP).

## 12.0 Ethics

### 12.1. Independent Ethics Committee (IEC) or Institutional Review Board (IRB)

The participating centers have their IRB/IEC (or an IRB/IEC tutoring them) established and authorized by the respective authorities, whose composition is available to them and is not shown here.

The Principal Investigator at each site is responsible for obtaining IRB/IEC approval for the final protocol, informed consent form and patient information sheet, any advertisements to recruit subjects, and documents to be handed out to the subjects at the next available meeting.

Written approval of these documents must be obtained from the committee before any subject is enrolled at a site.

When in accordance with local regulations IRB/IEC submission and interaction can be also covered by the assigned CRO.

Each investigator will also be responsible for complying with ethical standards for clinical trials as per local and European laws and regulations, during the study.

### 12.2. Ethical Conduct of the Study

This study will be conducted with the highest respect for the individual participants (i.e., subjects) according to the protocol, the ethical principles that have their origin in the Declaration of Helsinki (18th World Medical Assembly, 1964) and its last revision (Fortaleza, October 2013), the ICH Harmonized Tripartite Guideline for GCP and local laws and regulations of the country where the study is performed (Taiwan).

### 12.3. Subject Information and Consent

Written consent documents will embody the elements of informed consent as described in the Declaration of Helsinki and the ICH Guidelines for GCP and will be in accordance with all applicable laws and regulations. The informed consent form, subject authorization form (if applicable), and subject information sheet (if applicable) describe the planned and permitted uses, transfers, and disclosures of the subject's personal and personal health information for purposes of conducting the study. The informed consent form and the subject information sheet (if applicable) further explain the nature of the study, its objectives, and potential risks and benefits, as well as the date informed consent is given. The informed consent form will detail the requirements of the participant and the fact that he or she is free to withdraw at any time without giving a reason and without prejudice to his or her further medical care.

The investigator is responsible for the preparation, content, and IRB or IEC approval of the informed consent form and if applicable, the subject authorization form. The informed consent form, subject authorization form (if applicable), and subject information sheet (if applicable) must be approved by both the IRB or IEC and the sponsor prior to use.

The informed consent form, subject authorization form (if applicable), and subject information sheet (if applicable) must be written in a language fully comprehensible to the prospective subject.

It is the responsibility of the investigator to explain the detailed elements of the informed consent form, subject authorization form (if applicable), and subject information sheet (if applicable) to the subject. Information should be given in both oral and written form whenever possible and in the manner deemed appropriate by the IRB or IEC. In the event the subject is not capable of rendering adequate written informed consent, then the subject's legally acceptable representative may provide such consent for the subject in accordance with applicable laws and regulations.

The subject, or the subject's legally acceptable representative, must be given ample opportunity to: (1) inquire about details of the study and (2) decide whether or not to participate in the study. If the subject, or the subject's legally acceptable representative, determines he or she will participate in the study, then the informed consent form and subject authorization form (if applicable) must be signed and dated by the subject, or the subject's legally acceptable representative, at the time of consent and prior to the subject entering into the study. The subject or the subject's legally acceptable representative should be instructed to sign using their legal names, not nicknames, using blue or black ballpoint ink. The investigator must also sign and date the informed consent form and subject authorization (if applicable) at the time of consent and prior to subject entering into the study; however, the sponsor may allow a designee of the investigator to sign to the extent permitted by applicable law.

Before being enrolled in the clinical study, subjects must consent to participate after the nature, scope and possible consequences of the clinical study have been explained in a form understandable to them.

The investigator will provide the subject with an information form on the product and the study characteristics that should be read to and/or discussed with the subject in an understandable way. In this document, the subjects willing to consent to participate in this study will be informed of the nature, extent, design and conduct of the study and their consent will be obtained in writing prior to inclusion to the study schedule. Subjects will be given the opportunity to ask questions and will be informed of their right to withdraw from the study at any time, for any reason.

After reading the informed consent document, the subject must give consent in writing. The consent must be confirmed at the time of consent by the personally dated signature of the subject and the personally dated signature of the person conducting the informed consent discussions. A copy of the subject information sheet and the signed consent forms must be given to the subjects. The original signed consent will be retained in the investigator's site file.

The principal investigator will not undertake any measures specifically required only for the clinical study until valid consent has been obtained.

The investigator will not include in the study any subject without previously obtaining written consent from the subject.

#### **12.4. Confidentiality**

The sponsor and designees affirm and uphold the principle of the subject's right to protection against invasion of privacy. Throughout this study, a subject's source data will only be linked to the sponsor's clinical study database or documentation via a unique identification number. As permitted by all applicable laws and regulations, limited subject attributes, such as sex, age, or date of birth, and subject initials may be used to verify the subject and accuracy of the subject's unique identification number.

To comply with ICH Guidelines for GCP and to verify compliance with this protocol, the sponsor requires the investigator to permit its monitor or designee's monitor, representatives from any regulatory authority (e.g., FDA, Medicines and Healthcare products Regulatory Agency, Pharmaceuticals and Medical Devices Agency), the sponsor's designated auditors, and the appropriate IRBs and IECs to review the subject's original medical records (source data or documents), including, but not limited to, laboratory test result reports, ECG reports, admission and discharge summaries for hospital admissions occurring during a subject's study participation, and autopsy reports. Access to a subject's original medical records requires the specific authorization of the subject as part of the informed consent process.

Copies of any subject source documents that are provided to the sponsor must have certain personally identifiable information removed (i.e., subject name, address, and other identifier fields not collected on the subject's eCRF).

#### **12.5. Insurance Policy**

Daiichi Sankyo Co. Ltd. will obtain liability insurance, in accordance with the national requirements established in the laws of Taiwan, which covers health impairments resulting from medications and/or substances/investigational products administered in the course of this study for which the subject has given his/her written informed consent to participate.

### **13.0 Source Documents and Case Report Form Completion**

#### **13.1. Source Documents**

According to the guidelines on Good Clinical Practice, the Monitors Team must check the electronic case report form (eCRF) entries against the source documents, except for the pre-identified source data directly recorded in the eCRF.

During the study, the investigator will maintain adequate records for the study, including medical records, records detailing the progress of the study for each subject, laboratory reports, eCRFs, signed informed consent forms, drug disposition records, AE reports, and information regarding subject discontinuation and completion of the study.

The Informed Consent Form will include a statement by which the subject allows the Sponsor's duly authorized personnel, the IRB/IEC, and the regulatory authorities to have direct access to source data which supports the data on the eCRF (e.g., subject's medical file, appointment books, original laboratory records, etc.). These personnel, bound by professional secrecy, will not disclose any personal identity or personal medical information.

The process for source data verification will be documented in the monitoring plan.

#### **13.2. Case Report Forms**

The investigator must keep a written or electronic file for each subject that participates in the clinical trial. In that file, the subjects' demographic and medical data, especially: name, birthday, gender, medical history, diseases and concomitant drug, physical examination and clinical signs, observed adverse events, etc. should be recorded. It must be possible, in any moment, to identify the subject with his/her personal file. The period that the subject participates in the clinical trial must be clearly specified. The data collection will be done using the Electronic Data Capture (EDC) market leader tool from Medidata® called RAVE®. The RAVE® platform has been validated according to the highest industry standards and practices. The InForm® software uses a secure web browser to provide access to clinical study data and management of the clinical study process.

All documentation will be transcribed to an electronic CRF (eCRF). Any created documentation, especially the files that would be created by the technicians, must be filed. This includes the results of laboratory tests, ECGs, etc. These documents must be identified with the subject number, date of making and study code, in order to specify clearly the subject to whom this document belongs, and to identify the participants.

The main objective is to get the most complete files of each candidate.

Any result obtained during the study development will be reported in the subject's electronic case report form, and if it is used, the serious adverse event form must be sent to Daiichi Sankyo Taiwan Ltd.

The investigator will guarantee that all the documents sent to Daiichi Sankyo Taiwan Ltd., including the eCRF and other type of documents, do not contain any mention to the name of the subject. It is an investigator's duty to guarantee adequate filing and storage of the study documentation after the end of the study as specified in the Guidelines for Good Clinical Practice.

All the original files must be kept as much as possible following the hospital rules, research institutes or local regulation, but for at least 25 years according to the legislation in force.

All the eCRFs must be completed in its entirety. Any correction or amendment will be corrected by the investigator and the previous value recorded in the audit trail of the EDC system along with the reason and date of the change.

The eCRF is considered an official document, and it must be available for the Health Authorities.

Additional information on the data management and quality process is included in [Section 13.0](#) and [Section 15.0](#).

### **13.3. Monitoring**

Representatives of Sponsor must be allowed to visit all study site locations periodically to assess the data quality and study integrity. They will review study records on site and will compare them with source documents. They will also discuss the conduct of the study with the Investigator, and will verify that the facilities remain compliant with the study requirements.

#### 14.0 Data Quality Assurance

For the purpose of ensuring compliance with the protocol, Good Clinical Practice (GCP) and applicable regulatory requirements, the sponsor's Quality Assurance department (or authorized representatives) may conduct on site audits of all aspects of the clinical study either during the study or after the study has been completed. The investigator/institution will permit study related monitoring, audits, IRB/IEC review and regulatory inspection(s) by providing direct access to source documents.

The Investigator agrees to allow the auditors/inspectors to have direct access to his/her study records for review, being understood that these personnel are bound by professional secrecy, and as such will not disclose any personal identity or personal medical information.

As soon as the Investigator is notified of a future inspection by the authorities, he will inform the Sponsor and authorize the Sponsor to participate at this inspection.

The confidentiality of the data verified and the anonymity of the subjects should be respected during these inspections.

The study will be conducted with an electronic case report form with a qualified single data entry performed by the investigators with controlled and restricted access. Additional information on the data management will be provided in a specific document (Data Handling Manual [DHM]). A full data validation plan will be performed and described in this DHM which should be approved before the data entry process starts.

The database quality will be assessed before the database closure; and only when the Statistical Analysis Plan (SAP) is approved and the populations are determined, the database will be locked and moved to Statistics to perform the statistical analysis and prepare the Clinical Study Report (CSR).

Additional information on the data management process is included in [Section 16.0](#).

## 15.0 Practical Issues

### 15.1. Early Termination of the Study

The sponsor can prematurely terminate or suspend the study. Study sites will be closed upon study completion.

The investigator may initiate site closure at any time, provided there is reasonable cause and sufficient notice is given in advance.

Reasons for discontinuation of the study may include but are not limited to the following:

- The risks and benefits of the study are re assessed.
- The incidence of AEs constitutes a potential health hazard.
- New scientific data on the investigational medication do not justify a continuation of the clinical study.
- Serious and/or persistent non adherence to the protocol, GCP, and/or applicable regulatory requirements by an investigator/institution occurs.
- Subject enrolment is unsatisfactory.
- The IRB/IEC or other regulatory authority decides to terminate or suspend approval for the investigation or investigator.

Additionally, the sponsor has the right to terminate the study for any reason at any time.

If the study is prematurely terminated or suspended for any reason, the investigator has to inform the subjects and assure appropriate follow up for the subjects. The sponsor should promptly inform the investigators or institutions and the regulatory authorities of the termination or suspension and the reasons for the termination or suspension within the timeframes referred to in applicable regulations. The IRB/IEC should also be informed promptly and provided the reasons for the termination or suspension by the sponsor or by the investigator or institution as specified by the applicable regulatory requirements.

The last visit of the last patient (LPLV) indicates the end of the study and that end of study will be communicated to the IRBs/IECs and the regulatory authorities of each participating country. Last visit of the last subject at each site/country also indicates the end of the study for that site/country.

### 15.2. Publication Policy

The investigator is obliged to provide the sponsor with complete test results and all data derived by the investigator from the study. During and after the study, only the sponsor may make study information available to other study investigators or to regulatory agencies, except as required by law or regulation. Except as otherwise allowable in the clinical study site agreement, any public disclosure (including publicly accessible websites) related to the protocol or study results, other than study recruitment materials and/or advertisements, is the sole responsibility of the sponsor.

The sponsor may publish any data and information from the study (including data and information generated by the investigator) without the consent of the investigator. Manuscript authorship for any peer-reviewed publication will appropriately reflect contributions to the production and

review of the document. All publications and presentations must be prepared in accordance with this section and the Clinical Study Site Agreement. In the event of any discrepancy between the protocol and the Clinical Study Site Agreement, the Clinical Study Site Agreement will prevail.

#### **15.2.1 Clinical Trial Registration**

In order to ensure that information on clinical trials reaches the public in a timely manner and to comply with applicable laws, regulations and guidance, Daiichi Sankyo Taiwan Ltd. will, at a minimum register interventional clinical trials it sponsors anywhere in the world on ClinicalTrials.gov or other publicly accessible websites before start of study. Daiichi Sankyo Taiwan Ltd. contact information, along with investigator's city, and recruiting status will be registered and available for public viewing.

#### **15.2.2 Clinical Trial Results Disclosure**

Daiichi Sankyo Taiwan Ltd. will post the results of clinical trials on ClinicalTrials.gov or other publicly accessible websites, as required by Daiichi Sankyo Taiwan Ltd. Policy/Standard, applicable laws and/or regulations.

## **16.0 Data Management Procedures**

The full details of procedures for data handling will be documented in the Data Management Plan. AEs, medical history, and concurrent conditions will be coded using the Medical Dictionary for Regulatory Activities (MedDRA). Drugs will be coded using the World Health Organization Drug Dictionary.

### **16.1. Review and Confirmation of Case Report Forms**

Electronic case report forms will be filled directly by the investigators.

Prior to obtaining the clean file, checks of consistency of inclusion/non-inclusion criteria, clinical assessment, visit dates, compliance, concomitant treatment, adverse event, withdrawal information and efficacy evaluation (antiplatelet effect) will be performed.

Data query forms will be generated to the investigator in order to clarify the data inconsistencies through the source data verification.

### **16.2. Database production and verification**

#### **16.2.1 Data Management Plan**

A validation plan is set-up according to the protocol requirements, which describes the validation rules to be applied, in addition to the SAE reconciliation process between the clinical database and the safety database (Argus). Actions that should be taken in case of data abnormalities are detailed. In case of missing values, out of range values, data inconsistencies or values that fail logical checks, correction forms (queries) are edited and transmitted to the investigator for clarification.

#### **16.2.2 Database**

A database will be created in order to collect all clinical and other data from the clinical trial. The data management will take place at the Data Management Department of Linical.

#### **16.2.3 Database access**

Access to the database will be restricted to the investigators, data managers and clinical monitors. Any entry in the database will be traceable through its identification and date. Audit trail of data changes will be assured.

#### **16.2.4 Quality and consistency controls**

The investigators will enter the clinical data in the electronic case report form.

Prior to obtaining the clean file, checks of consistency of inclusion/exclusion criteria, clinical assessment, visit dates, compliance, concomitant treatment, adverse event, withdrawal information and efficacy evaluation (antiplatelet effect) will be performed.

### 16.2.5 Data queries

Data query forms will be generated to the investigator in order to clarify the data inconsistencies through the source data verification.

Only then and after all detected errors, inconsistencies or doubts cleared, will the database be declared a clean file and protected accordingly.

### 16.2.6 Clean File

A clean file will be created and registered, to which further changes will be disallowed. A document with the eligibility of subjects will be generated.

### 16.2.7 Data coding

Coding will be carried out according to standard dictionaries partly by program and then validated and completed by a medical doctor according to the Linical dictionaries. The latest available version of the following dictionaries will be used:

- Concomitant treatments: WHO DRUG
- Adverse Events: MedDRA

All case report forms and data checking records will be retained as permanent records of the study.

## 18.0 Appendices

### 18.1. Schedule of Assessments

← Period 1      ← Period 2      →

VISITS Week	V1 Screening	V2 Day 1	V3 Week 4	V4 Week 16	End of Study Early Termination 	
					V5 Week 28	OPTIONAL V6 Maximum 12 months of P2Y 12 inhibitor treatment after ACS underwent PCI
Study days (allowed deviation days in brackets)	D-28 to D-1	D1	D28 (± 14)	D112 (± 14)	D196 (± 28)	D365 (-28)
Informed consent	X					
Demographics	X					
Inclusion and exclusion criteria	X	X				
Medical history	X					
Physical examination	X	X	X	X	X	X
Vital signs (including blood pressure)	X	X	X	X	X	X
Pregnancy test	X				X	X
Safety laboratory tests	X	X 	X 	X 	X 	X 
Blood sample for CYP2C19 genotyping			X 			
Electrocardiogram	X		X		X	X
P2Y 12 reaction unit (PRU)		X 	X 			
HTPR		X 	X 			
Platelet inhibition (%)		X 	X 			
Major bleeding events		X	X	X	X	X
Minor and clinically relevant bleeding events		X	X	X	X	X
Major adverse cardiovascular events (MACE)		X	X	X	X	X
All cause death		X	X	X	X	X
Prasugrel Maintenance Dose (MD) + aspirin		X	X	X	X	X
Pre-treatment adverse events 	X	X 				
Treatment emergent adverse events 		X 	X	X	X 	X 
Previous medication	X					
Concomitant medication		X	X	X	X	X

- (1) Patients who signs the pharmacogenomic informed consent form separately will preserve a blood sample for CYP2C19 genotyping  
 (2) Safety lab sample to be done before prasugrel MD + aspirin administration of each corresponding visit.  
 (3) PRU to be done immediately before prasugrel MD + aspirin administration on Day 1  
 (4) PRU to be done immediately before prasugrel MD + aspirin administration on Visit 3 (Week 4)  
 (5) Adverse Events will be collected since the informed consent signature until last study visit  
 (6) Pre-treatment adverse events will be considered since signature date to the date of 1st MD prasugrel administration (until pre-dosing)  
 (7) Treatment emergent events will be considered since 1st MD prasugrel administration (post-dosing) until last MD prasugrel administration + 14 days  
 (8) Safety follow-up will be extended for patients with AEs at the last visit until the event is resolved or stabilized  
 (9) For subject who terminated before Visit 3, Platelet function tests have to be conducted during the early termination visit

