#### **8.4.1.8 Electrocardiogram, heart rate, blood pressure**

A 12-lead ECG will be performed locally at screening (visit 1), treatment week 4 (visit 3), treatment week 28 (visit 5), optionally based on investigator's discretion at maximum 12 months of P2Y12 inhibitor treatment after ACS underwent PCI (visit 6) or early termination. Additional ECGs may be performed at the discretion of the investigator during any follow-up. The findings and any abnormality will be recorded in the eCRF as either medical history (findings at screening) or adverse events (any further finding or change from screening). Standard ECG parameters will be recorded in the eCRF (heart rate, RR, QT, QTc following both Bazzett's and Fridericia's methods).

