## 9.0 Adverse Events (AEs)

### 9.1 Definitions

#### 9.1.1 Adverse Event

An adverse event (AE) is defined as any unfavorable and unintended sign (including a clinically significant abnormal laboratory finding), symptom or disease, temporally associated with the use of a medicinal product, regardless of its nature, intensity, seriousness, or presumed relationship (causality) to the product or experimental procedure used.

Adverse Events will be collected since the informed consent signature, and all adverse events which occur after the first study medication intake and within 14 days after the treatment stop date will be considered as treatment emergent adverse events (TEAEs).

Each TEAE will be evaluated for duration, intensity, and relationship to (or association with) the study treatment (or other causes). Additionally, the actions taken (e.g., administration of treatment) and the resulting outcome of the adverse event will be indicated on the eCRF. All adverse events will be followed up until resolved or as clinically required.

Only subjects with an ongoing AE at the last study visit will be followed-up for safety reasons until the event is resolved or stabilized.

**Any AE, which remains unresolved after completion of the trial, requires detailed evaluation and follow-up until the AE has been resolved or a reasonable explanation for its persistence is found.**

If a worsening of any pathological condition that the subject had before the start of the study or medical problems that are present prior to the start of treatment but worsen during treatment occur, these must be considered as a new adverse event and will require a complete evaluation and the relevant explanation in the case report form.

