#### 9.1.2 Additional Points to Consider for AEs

An untoward finding generally may:

- Indicate a new diagnosis or unexpected worsening of a pre-existing condition. (Intermittent events for pre-existing conditions or underlying disease should not be considered AEs.)
- Necessitate therapeutic intervention.
- Require an invasive diagnostic procedure.
- Require discontinuation or a change in dose of study medication or a concomitant medication.
- Be considered unfavorable by the investigator for any reason.
- AEs caused by a study procedure (e.g., a bruise after blood draw) should be recorded as an AE.

Diagnoses vs signs and symptoms:

- Each event should be recorded to represent a single diagnosis. Accompanying signs (including abnormal laboratory values or ECG findings) or symptoms should NOT be recorded as additional AEs. If a diagnosis is unknown, sign(s) or symptom(s) should be recorded appropriately as an AE(s).

Laboratory values and ECG findings:

- Changes in laboratory values or ECG parameters are only considered to be AEs if they are judged to be clinically significant (i.e., if some action or intervention is required or if the investigator judges the change to be beyond the range of normal physiologic fluctuation). A laboratory re-test and/or continued monitoring of an abnormal value are not considered an intervention. In addition, repeated or additional noninvasive testing for verification, evaluation or monitoring of an abnormality is not considered an intervention.
- If abnormal laboratory values or ECG findings are the result of pathology for which there is an overall diagnosis (e.g., increased creatinine in renal failure), the diagnosis only should be reported appropriately as an AE.

Pre-existing conditions:

- Pre-existing conditions (present at the time of signing of informed consent) are considered concurrent medical conditions and should NOT be recorded as AEs. Baseline evaluations (e.g., laboratory tests, ECG, X-rays etc.) should NOT be recorded as AEs unless related to study procedures. However, if the subject experiences a worsening or complication of such a concurrent condition, the worsening or complication should be recorded appropriately as an AE. Investigators should ensure that the event term recorded captures the change in the condition (e.g., “worsening of...”).

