#### 9.6. Adverse Event Collection Period

Adverse events will be collected throughout the whole study period (screening of 4 weeks, treatment period 1 of 4 weeks, treatment period 2 of +24 weeks (optionally up to a maximum 12 months of P2Y12 inhibitor treatment after ACS underwent PCI), and safety follow-up if needed).

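### Two adverse-event counting rules need reconciling: one ECG sentence contradicts the general AE rule, and the TEAE window runs 14 days past planned AE collection

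*Combined protocol and SAP*

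**What the plan says.** **ECG findings.** Section 8.4.1.8 sends screening findings to medical history and later ones to "adverse events (any further finding or change from screening"; it sets no threshold of significance. Section 9.1.2 says: "Changes in laboratory values or ECG parameters are only considered to be AEs if they are judged to be clinically significant". Section 8.4.1.7 treats laboratory values as 9.1.2 does: an out-of-range value becomes an AE only if the investigator finds it clinically relevant. ECGs are scheduled at screening, week 4, week 28 and optional Visit 6, or at early termination.

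**Time window.** Section 9.1.1 says that events after the first dose and "within 14 days after the treatment stop date will be considered as treatment emergent adverse events (TEAEs"). Footnote 7 of the schedule (18.1) agrees: "until last MD prasugrel administration + 14 days". Footnote 5, attached to the same row of the schedule, sets the collection period: "Adverse Events will be collected since the informed consent signature until last study visit". Section 9.6 words it differently ("Adverse events will be collected throughout the whole study period") and adds safety follow-up where needed. On who is followed after the last visit, 9.1.1 says: "Only subjects with an ongoing AE at the last study visit will be followed-up for safety reasons until the event is resolved or stabilized". Footnote 8 says the same in substance.

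**Endpoint.** Sections 6.2.1.2 and 6.2.2.2 name adverse events as a secondary endpoint in Periods 1 and 2. Sections 11.1.4.2.1 and 11.1.4.2.2 report the percentage with a 95% confidence interval. These sections speak of adverse events and never of TEAEs.

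**The concern.** The AE percentage is only interpretable if every site applies the same rule for what is an AE and the data are collected for as long as events count. With about 10 sites, one site may record every new ECG finding under 8.4.1.8 while another records only significant ones under 9.1.2. Both would be following the protocol, yet their AE percentages would not be comparable. The week 4 ECG brings this into Period 1, and the later ECGs bring it into Period 2.

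The window problem is of a different kind. The definition of a TEAE is consistent, but the planned collection is too short to fill it. A subject who finishes treatment with no ongoing AE has no planned contact during the last 14 days in which an event would count. A first AE in those days would be known only if it happened to be reported. In addition, the analysis sections do not say whether those days belong in the reported percentage.

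**Working it through.** **1. The plan's own AE figure.** Section 11.2 uses n = 170 and an incidence of 0.01. P(at least one event) = 1 − 0.99^170 = 0.819, which reproduces the stated 82%. The 0.82% in the same paragraph is a misprint of this figure.

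**2. ECG rules side by side.** Under 8.4.1.8, a non-significant ECG change at week 4 is an AE. Under 9.1.2 it is not. No section says which prevails, so this is a direct contradiction. The laboratory rule in 8.4.1.7 agrees with 9.1.2, so the conflict is confined to ECGs.

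**3. Possible size of the ECG conflict.** The documents give neither an AE rate nor a rate of ECG changes, so both are assumed. Let q be the AE percentage under 9.1.2, and e the share of the remaining subjects who have only a non-significant ECG change. The percentage under 8.4.1.8 is q + (1 − q)e.

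| q | e = 2% | e = 5% | e = 10% | e = 20% |
|---|---|---|---|---|
| 30% | 31.4% | 33.5% | 37.0% | 44.0% |
| 50% | 51.0% | 52.5% | 55.0% | 60.0% |

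**4. Length of the uncollected tail.** The schedule marks prasugrel at Visits 5 and 6, and footnote 2 reads "Safety lab sample to be done before prasugrel MD + aspirin administration of each corresponding visit". A completer's last dose therefore falls at about the last visit. With T days from first dose to Visit 5, the tail is 14/(T + 14) of the TEAE window:

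- Day 168 (earliest allowed): 14/182 = 7.7%
- Day 196 (nominal): 14/210 = 6.7%
- Day 224 (latest allowed): 14/238 = 5.9%

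**5. Effect on the Period 2 percentage.** Assume a constant hazard of a first AE. If q is the percentage counted to Day 196, the percentage counted to last dose + 14 days is 1 − (1 − q)^(210/196).

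| To last visit | To last dose + 14 days | Difference (points) |
|---|---|---|
| 10% | 10.7% | 0.7 |
| 30% | 31.8% | 1.8 |
| 50% | 52.4% | 2.4 |
| 70% | 72.5% | 2.5 |

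For scale, with 200 treated subjects and a true 30%, the half-width of the 95% interval is 1.96 × √(0.3 × 0.7/200) = 6.4 points.

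**6. Effect on the detection figure.** If the 0.01 incidence refers to the whole TEAE window, the incidence seen by Day 196 is 1 − 0.99^(196/210) = 0.00934. The detection probability is then 1 − (1 − 0.00934)^170 = 79.7% (79.3% for Day 168, 80.0% for Day 224).

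**7. Period 1.** For a subject who continues past week 4, no post-treatment tail has begun, so the window mismatch hardly touches the Period 1 percentage.

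**The case against.** A TEAE definition classifies events and need not set how long they are collected. It still has work to do when the last dose precedes the last visit. The protocol also leaves room for late reports: 8.4.2 allows unscheduled visits and telephone contacts that include safety assessment during follow-up, 9.6 allows follow-up if needed, and 11.1 defers full analysis detail to a statistical analysis plan. The percentage is descriptive, from a single arm.

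Much of this stands. The window texts are a mismatch, not rival definitions, and late events are not wholly beyond reach. But the unscheduled visits are discretionary, and the calls have no stated day, question list or population. Neither is a planned contact for a subject without an ongoing AE. A later analysis plan can define the percentage, but it cannot recover events that nobody collected.

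A reader might also infer stronger points that the documents do not support:

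- *A third of the window is lost for week 4 stoppers* (14/42 = 33%). This assumes that the early-termination visit falls on the last-dose day. Neither 8.4.2 nor 8.5.2 sets that timing, and a later visit would cover part or all of the 14 days. Section 9.3 also follows anyone withdrawn for an AE until its outcome is known.
- *Uneven follow-up distorts the percentage because late events are found in subjects who already had an AE.* Those subjects are already in the numerator, so further events cannot change a subject-level percentage.
- *Most patients will show some ECG change.* The documents give no such rate.
- *Bleeding, cardiovascular events and deaths share the gap.* They are separate endpoints with no 14-day window.

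**Conclusion.** The point holds as two matters of reconciliation. The ECG contradiction is the firmer one: it is explicit, no section resolves it, and it affects the AE percentage in both periods. Its size is unknown. Under the assumed shares it adds 1 to 14 points to an AE percentage of 30% to 50%, which at the upper end exceeds the sampling error of the estimate.

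The window mismatch is real but probably small: about 0.7 to 2.5 points on the Period 2 percentage. That range assumes a constant hazard, AE rates of 10% to 70%, a last dose at Day 196 on the day of the last visit, and no late events reported spontaneously. It is well inside the 6.4-point half-width at 30%. It also counts as a shortfall only if the percentage is meant to include the tail, which the analysis sections do not say. The PRU primary endpoint and the sample size are unaffected.

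**What to change.** 1. **ECG.** Replace the recording sentence in 8.4.1.8 with a reference to the clinical-significance rule in 9.1.2.
2. **Window.** Choose one of two routes:
   - Fix one of the telephone contacts already provided for in 8.4.2 at 14 days after the last dose for every treated subject, with AE questions. Amend footnotes 5 and 8, section 9.1.1 (the sentence limiting follow-up to ongoing AEs) and section 9.6 to match.
   - Or end the TEAE window at the earlier of the last study visit and last dose + 14 days, in both 9.1.1 and footnote 7. Taking the earlier date keeps the post-dose cap for subjects whose last visit comes well after their last dose.
3. **Analysis.** In either case, state in 11.1.4.2 whether the AE percentage means TEAEs and whether the 14-day tail is included.

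The cost is wording, plus at most one call per subject under the first route. The second route costs no contact but gives up information on events just after prasugrel stops.
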